## **7.7. Glomerular Filtration Rate Estimation**

Significant changes in laquinimod exposure, in particular in terms of unbound drug fraction, are predicted in patients with moderate and severe renal impairment (see Section 1.3.2.1). Consequently, GFR will be estimated at all visits to monitor renal function in the study in order to identify patients with potentially impaired laquinimod clearance. Patients with a confirmed GFR  $\leq 60$  mL/min/1.73 m^2 should stop study medication temporarily and the GFR assessment should be repeated. If the renal impairment is confirmed (GFR  $\leq 60$  mL/min/1.73 m^2), the patient should stop study medication permanently (see Section 3.6.5).

Following recent findings connecting Gd-based contrast agents and nephrogenic systemic sclerosis, the GFR result should be available prior to the baseline MRI scan. GFR estimation will be done in accordance with the central laboratory creatinine value measurement performed at the screening visit. The central laboratory will report estimated GFR; however, if the result is not available prior to the baseline MRI scan, the CKD-EPI Creatinine Equation (2009) from the following online GFR calculator should be used by the investigator:

[http://www.kidney.org/professionals/kdoqi/gfr\\_calculator.cfm](http://www.kidney.org/professionals/kdoqi/gfr_calculator.cfm)

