### **3.6.5. Renal Impairment**

To avoid exposures to higher levels of laquinimod (see Section 1.3.2.1), a stopping rule related to renal impairment has been introduced. Patients who develop renal disease associated with moderate or severe functional impairment, defined as glomerular filtration rate (GFR)  $\leq 60$  mL/min/1.73 m^2, while participating in the study should stop study medication temporarily and the GFR assessment should be repeated. If the renal impairment is confirmed (GFR  $\leq 60$  mL/min/1.73 m^2), the patient should stop study medication permanently.

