h Serum chemistry (including electrolytes, fibrinogen, glucose, urea, creatinine, alanine aminotransferase, aspartate aminotransferase, gamma-glutamyl transpeptidase, alkaline phosphatase, creatine phosphokinase, C-reactive protein, pancreatic amylase [lipase will be tested in case of abnormal pancreatic amylase results], total protein, albumin, direct and total bilirubin) and complete blood count (CBC) with differential. Coagulation to be tested only if required according to Guidance on Safety Monitoring.

i Unscheduled urgent safety laboratory samples, pharmacokinetic blood samples, and/or samples for potential biomarker analysis may be collected at the discretion of the investigator or medical monitor at any time to assist with further investigations of cardiovascular events or other clinical event of interest. The samples should be collected as soon as possible in association with the event.

j Fasting lipid profile includes total cholesterol, HDL, LDL (measured), and triglycerides.

k Patients who develop renal disease associated with moderate or severe functional impairment, defined as glomerular filtration rate (GFR)  $\leq 60$  mL/min/1.73 m^2, while participating in the study should stop study medication temporarily and the GFR assessment should be repeated. If the renal impairment is confirmed (GFR  $\leq 60$  mL/min/1.73 m^2), the patient should stop study medication permanently.

l For women of child-bearing potential serum  $\beta$ -hCG test will be done at each scheduled study visit. Urine  $\beta$ -hCG tests will be done at each study visit; in case of a positive result, study drug should not be dispensed until the serum  $\beta$ -hCG result is available. At baseline, serum  $\beta$ -hCG will be done within 7 days prior to randomization, such that the result is available prior to the first dose; urine  $\beta$ -hCG test will also be done on site prior to the first dose.

m Starting from week 12 visit, women of child-bearing potential will be provided with home pregnancy urine  $\beta$ -hCG test kits and will be instructed how to perform the test. The site staff will schedule the home test to be performed every 28  $\pm$ 2 days between study visits.

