### **3.11.3. Scheduled Treatment Visits (Visits 1 to 6, Weeks 4 to 48, and Every 12 weeks Thereafter)**

Following the baseline visit, patients will return to the study center at weeks 4, 8, 12, and every 12 weeks thereafter until completion. A week is defined as  $7 \pm 2$  days.

Procedures for study completion are detailed in Section 3.11.5.

The following procedures and evaluations will be performed at these visits:

- Call IVRS/IWRS.\*
- Vital signs (temperature, pulse, BP)
- Weight\*
- Physical examination.
- ECG (weeks 4, 8, 12, 24, and every 24 weeks thereafter)
- Review concomitant medications.
- Record adverse events.
- Patient compliance (study drug accountability) and study drug dispensing.\*
- Safety laboratory tests:
  - serum pregnancy test ( $\beta$ -hCG) for women of child-bearing potential.\*
  - Urine pregnancy test ( $\beta$ -hCG) for women of child-bearing potential. In case of positive result, study drug should not be dispensed, until results of serum  $\beta$ -hCG test are available. The rest of the visit activities should be performed.\*
  - Starting from week 12 visit, between study visits, women of child-bearing potential will be provided with home pregnancy urine  $\beta$ -hCG test kits and will be instructed how to perform the test. The site staff will schedule the home test to be performed every  $28 \pm 2$  days. To verify whether the test has been performed and to record the result of the test, a mandatory phone call will be performed by the Treating Neurologist or by the site's nurse/study coordinator within 72 hours after the test was scheduled to be performed and the patient will be asked specific questions regarding the test. In case of a suspected pregnancy (positive urine  $\beta$ -hCG test result, delay of menstruation or any other reason suggesting pregnancy), the caller will ensure that the study drug has been stopped and the patient will be instructed to arrive to the study site as soon as possible (within 10 days) for further evaluations with the remaining study medications.\*
  - CBC with differential.
  - In case of hemoglobin decrease of  $>1$  g/dL from the patient's hemoglobin level at baseline:
    - patient will be re-tested to confirm decrease
    - if decrease confirmed, a thorough anemia work-up will be done including:
      - directed medical history and physical examination

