### 7.3.3. Anemia Panel

The anemia panel is assessed at baseline and also at 1 subsequent time point (with B12) if hemoglobin decrease of >1 g/dL from the patient's hemoglobin level at baseline and the decrease is confirmed.

- At baseline: blood smear, serum iron, ferritin, total iron binding capacity, folic acid, haptoglobin, IL-1, IL-6, interferon IFN- $\gamma$ , TNF- $\alpha$ , and hepcidin.
- In case of hemoglobin decrease of >1 g/dL from the patient's hemoglobin level at baseline:
  - patient will be re-tested to confirm decrease
  - if decrease confirmed, a thorough anemia work-up will be done including:
    - directed medical history and physical examination
    - anemia panel (blood smear, serum iron, ferritin, total iron binding capacity, folic acid, haptoglobin, IL-1, IL-6, IFN- $\gamma$ , TNF- $\alpha$ , and hepcidin) and B12
    - additional investigations and follow-up per the investigator's discretion or sponsor's request

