#### 1.1. Elevation of Either ALT or AST to $\geq 3 \times$ ULN:

Confirmation of the abnormality (in case the abnormality is of ALT or AST  $\geq 8 \times$ ULN, no confirmation is required prior to study drug discontinuation, but the assessments below should be performed):

- The day in which the abnormal value is received from the laboratory will be considered as Day 0.
- The Investigator should repeat the test before Day 2, for confirmation purposes (this may be performed in a local laboratory along with CBC and differential to assess for eosinophilia. In general, in case a blood sample is sent to a local laboratory, the following assessments [and reference ranges] are mandatory: ALT [serum glutamic pyruvic transaminase; SGPT], AST [serum glutamic oxaloacetic transaminase; SGOT], ALP, total bilirubin, CBC [with differential for eosinophil count, separate tube], and INR [separate tube; not to be sent in a confirmatory test]). The investigator should also question the patient regarding symptoms.

The abnormality will be regarded as confirmed in each of the following scenarios:

1. In case baseline value was within normal range and ALT or AST is still  $\geq 3 \times$ ULN
2. In case baseline value was above ULN and ALT or AST is  $\geq 2 \times$  the baseline value.

Upon confirmation of the abnormality as noted above, the following additional evaluations should be performed and results should be recorded in the CRF.

---

a Thorough medical history with a focus on liver disease: Personal or family history of liver disease; personal history of a systemic disease with potential liver involvement; exposure to alcohol, medications (prescription or OTC), herbal preparations, dietary supplements, recreational drugs, special diets or environmental chemical agents; potential exposure to infectious agents (eg, travel to developing countries, history of potential exposure to blood or blood products, high-risk sexual relations) and any additional information deemed relevant by the investigator. Physical examination – including signs of chronic liver disease

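### Protocol Section 7.7 makes the temporary renal hold depend on an already confirmed GFR of 60 or less, whereas the other four protocol statements of the rule need no confirmation before the hold

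*Protocol*

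**What the plan says.** Section 7.7 of the protocol requires GFR to be estimated at every visit and then restates the stopping rule. The people it holds are "Patients with a confirmed GFR" at or below 60 mL/min/1.73 m². They stop drug temporarily, the GFR is repeated, and if the impairment is confirmed, "the patient should stop study medication permanently (see Section 3.6.5".

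Section 3.6.5, under the safety guidelines and stopping rules, covers patients who develop renal disease with moderate or severe functional impairment, which it defines as GFR of 60 or less. They "should stop study medication temporarily and the GFR assessment should be repeated", and a confirmed value makes the stop permanent. Footnote k of Table 5 has the same trigger and sequence: "while participating in the study should stop study medication temporarily and the GFR assessment should be repeated". Footnote k of Table 6 and Appendix B item 7 match it. None of these four has the word 'confirmed' ahead of the hold. The schedule footnotes in the SAP (Tables 1 and 2, footnote k) carry the same wording as the four.

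**The concern.** The repeat test is what supplies confirmation, yet Section 7.7 requires confirmation before it starts the hold that precedes that test. The sentence is circular, and a site has to choose how to act on it.

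The choice matters because this is a dosing instruction. It was added when the 1.5 mg arm was stopped after cardiovascular events at the higher doses, to keep 0.6 mg patients from reaching higher exposure through organ impairment. Section 1.3.2.1 gives model-predicted unbound exposure at 0.6 mg of 1.65-fold in moderate and 1.86-fold in severe renal impairment. Dosing while a low GFR awaits its repeat is what the hold is meant to prevent. At stake are the timing of the hold and, in some patients, whether a permanent stop happens at all.

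**Working it through.** The plan states no figure here to reproduce. The check is a comparison of texts.

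**Step 1: count the statements.** Leaving out the summary of changes, the protocol states the rule five times: Sections 3.6.5 and 7.7, footnote k of Table 5, footnote k of Table 6, and Appendix B item 7. One of the five (Section 7.7) puts 'confirmed' ahead of the hold; four do not.

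**Step 2: what confirmation means elsewhere in the protocol.** For hemoglobin (Section 7.3.3), the "patient will be re-tested to confirm decrease". For liver enzymes (Appendix B, 1.1), "The Investigator should repeat the test before Day 2, for confirmation purposes". Where a stop needs no retest, as for ALT or AST at 8 times ULN or more, Appendix B says so: "no confirmation is required prior to study drug discontinuation". Reading 'confirmed GFR' as a retested GFR is therefore consistent with the protocol's own usage.

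**Step 3: apply both readings to the same results.** 'Low' means GFR of 60 or less. The right-hand column takes 'confirmed' in its retest sense.

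| Successive GFR results | Section 3.6.5 and the three matching statements | Section 7.7 read literally |
|---|---|---|
| low, then above 60 | hold at the first value; no permanent stop | no hold |
| low, low, above 60 | hold at the first, permanent stop at the second | hold at the second; no permanent stop |
| low, low, low | hold at the first, permanent stop at the second | hold at the second, permanent stop at the third |

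The readings differ in every row on when, or whether, the hold begins. In the second row they also differ on the permanent stop.

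**Step 4: look for a repeat interval.** Extra dosing under the literal reading is the time from the first to the second low value, at one dose a day. No section says when the GFR must be repeated. The calculation lacks its only input, so no number of doses follows from the documents.

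**The case against.** The best defence is that this is a single stray adjective that the document corrects itself. Section 7.7 deals with GFR estimation; the stopping rule belongs to Section 3.6.5, which Section 7.7 cites. Both visit-schedule footnotes and the safety guidance in Appendix B give the rule without the extra condition. If 'confirmed' already meant retested, the later clause about confirming the impairment would have little to do. Most of this stands, and it is why severity is low. It does not make Section 7.7 correct: the citation is attached to the permanent-stop sentence, not to the sentence that triggers the hold.

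Three stronger readings are tempting, and the documents do not support them.

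- *Section 7.7 puts the repeat before the hold, unlike the others.* It does not. All five statements place a hold before a repeat; the difference is the added condition for entering the hold.
- *Section 7.7 sets a rule of two low values for the hold and three for the permanent stop, against one and two elsewhere.* Section 7.7 states no count and describes no retest before the hold. The right-hand column in the working is an inference from a circular sentence. One and two is the natural reading of the other four, but they too are worded in terms of developing renal disease and do not count results.
- *The extra dosing can be sized.* A reader might borrow the liver-enzyme deadline and infer about 2 doses. Or, because "patients will return to the study center at weeks 4, 8, 12, and every 12 weeks thereafter until completion", a reader might infer 4 × 7 = 28 or 12 × 7 = 84 doses until the next scheduled visit. The deadline belongs to a different test. The visit-based figures assume that a site sees a low GFR and waits, although Section 3.11.6 allows unscheduled visits for laboratory follow-up.

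**Conclusion.** Section 7.7 is wrong as written, at low severity. It requires confirmation twice where the other four protocol statements require it once. Read literally, it can delay a safety hold and can miss a permanent stop that Section 3.6.5 requires.

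The size that the documents support is one discordant statement in five. The number of patients affected is not given, but should be small because exclusion criterion 26 removes anyone with GFR of 60 or less at screening. The consequence rests on two assumptions: that a site takes 'confirmed' in its retest sense, and that it acts on Section 7.7 without following the reference to Section 3.6.5. A site that treats the word as a drafting slip, which it probably is, gives no extra doses. Sample size, power and the efficacy analyses do not change.

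**What to change.** Delete the first 'confirmed' in Section 7.7, so that the hold starts at the first GFR of 60 or less pending the repeat, as in Section 3.6.5. Leave the later clause, which makes the stop permanent on confirmation, as it is. All five statements then agree. Tell sites of the correction in a short note.

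The cost is one word and one notice. The clinical downside is a few more temporary holds in patients whose repeat turns out to be above 60, and Section 3.6.5 already requires those holds.

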## **7.8. Cardiovascular Risk Assessment and Management**

Evaluation and management of major modifiable cardiac risk factors (eg, diabetes, high blood pressure, hyperlipidemia, tobacco smoking) will be performed at the time points indicated in Table 5 and Table 6. In addition, an evaluation should take place as soon as possible for patients already in the study, following approval of Global Amendment 2.

Cardiovascular risk management should be conducted according to evidence-based, local standard-of-care procedures. Patients will undergo referral to a suitable clinic if needed.

## **7.9. Other Safety Measures and Variables: Concomitant Therapy or Medication**

Concomitant therapy or medication usage will be monitored throughout the study. Details of prohibited medications are found in Section 5.2.

## **8. ASSESSMENT OF PHARMACOKINETICS/ PHARMACOGENOMICS/OTHER ANCILLARY STUDIES**

### **8.1. Pharmacokinetic Variables**

Samples will be analyzed for laquinimod using an appropriate validated method. Incurred sample reanalysis may be performed.

Blood samples (approximately 4 mL) will be collected from all patients at weeks 4, 8, 12, 24, and 48 for plasma concentration measurements of laquinimod.

Unscheduled pharmacokinetic blood samples may be collected at the discretion of the investigator or medical monitor at any time to assist with further investigations of cardiovascular events or other clinical event of interest. The samples should be collected as soon as possible in association with the event.

The dates and times of study drug administration and the date and time of each pharmacokinetic sample will be recorded on the source documentation and transcribed onto the CRF.

Pharmacokinetics of laquinimod will be evaluated in this study using a PPK approach. Details of blood sampling collection and processing are provided in the Laboratory Manual.

### **8.2. Potential Biomarker Measures**

Potential biomarker assessments to better understand laquinimod MoA, as well as to explore response predictive markers for efficacy or safety, may include 1) cytokines and other soluble marker levels; 2) gene and RNA expression; 3) proteomic profile; and/or 4) other relevant biomarkers.

Details of sample collection and processing are provided in the Laboratory Manual.

Analysis will be performed if and when required. Since new biomarker techniques continue to be developed, the method and laboratory that will be recommended cannot be anticipated.

Unscheduled samples for potential biomarker assessments may be collected at the discretion of the investigator or medical monitor at any time to assist with further investigations of cardiovascular events or other clinical event of interest. The samples should be collected as soon as possible in association with the event.

### **8.3. Pharmacogenomic Variables**

PGx studies investigate the association between genetic sequence polymorphisms and/or gene expression signatures and clinical response to a certain therapeutic intervention. It may help explaining inter-individual variability and subsequently identify population subgroups that respond differently to the drug. Furthermore, regulatory guidance and white papers indicate that PGx analyses employing DNA collected from all study participants may support investigation of unexpected adverse events.

In order to allow any subsequent analyses, appropriate samples will be requested from all patients in the study; however this can be omitted if considered unacceptable per local

regulations. PGx assessment might include DNA variations potentially associated with clinical treatment responses to laquinimod (eg, clinical effect, pharmacokinetics, tolerability, and safety features or disease susceptibility and severity features). The final list of genes that might be investigated will be selected at a later stage before the analysis so as to allow updating with new scientific information. Genomic analysis could also include a sequencing of the whole genome if required.

The PGx sample should be collected at baseline; if the sample is not obtained at baseline for any reason, it should be collected at the next possible visit.

## **8.4. Other Ancillary Studies**

### **8.4.1. Cerebrospinal Fluid (CSF) Assessment**

Putative neuroprotective effects of laquinimod will be explored in a subset of patients (only selected sites will participate) by analyzing CSF levels of axonal, neuronal, and/or inflammatory markers. CSF will be collected via lumbar puncture according to standard or local practice, using atraumatic needles. Additional detail can be found in the CSF Ancillary Study Manual.

CSF (to be performed in selected sites) will be collected from all patients who signed an appropriate, EC approved informed consent form, at week 48.

### **8.4.2. Optical Coherence Tomography (OCT) Evaluation**

OCT is a fast, non-invasive, interferometric technique that allows imaging of the retina, including the retinal nerve fiber layer (RNFL), which is principally composed of the axons of the ganglion cells that form the optic nerves. Since these axons are nonmyelinated until they penetrate the lamina cribrosa, the RNFL is an ideal structure for visualizing subtle processes of axonal degeneration.

Retinal degeneration in MS not only reflects a morphological correlate of the functional visual deficits in MS patients, but also mirrors the overall disability assessed by the EDSS and the BA measured by MRI. Therefore, OCT is an ideal tool for visualizing the processes of neurodegeneration, neuroprotection, and neurorepair in MS.

Additional detail can be found in [Appendix L](#) and the OCT Ancillary Study manual.

OCT (to be performed in selected sites) will be performed in all patients who signed an appropriate, EC approved informed consent form, at week 0 (can be performed up to 42 days prior to baseline), week 48 (or ET visit if performed after the week 24 visit and prior to week 48), and week 96 to assess retinal thickness.

## 9. STATISTICS

### 9.1. Study Design and Randomization

This study is a multinational, multicenter, randomized, double-blind, parallel-group, placebo-controlled study, to evaluate the efficacy, safety and tolerability of daily oral administration of laquinimod (0.6 or [until 01 January 2016] 1.5 mg) in patients with PPMS. Randomization will be as described in Section 3.3. The analyses described in Sections 9.6 and 9.8 will be performed using data collected during Part A (Core Study). Data collected during Part B may be used for additional exploratory analyses as will be described in a SAP, to be approved and signed prior to unblinding the Part A data.

### 9.2. Sample Size and Power Considerations

Sample size calculations were based on the following assumptions:

- 2-sided alpha level of 5%
- treatment difference (delta) of 0.3 in PBVC
- standard deviation of 0.8

Under the above assumptions 252 patients enrolled for 0.6 mg and placebo (126 per arm) will provide 84% power to detect a statistically significant result for 0.6 mg laquinimod arm comparison to placebo. To adjust for the anticipated 10% dropouts, the sample size was increased to 280 patients. Adding 95 patients on 1.5 mg yields a total of 375 patients.

